#### **7.10.2 Pharmacodynamic Analysis**

Not applicable.

#### **7.11 Other Outcomes**

Not applicable.

#### **7.12 Safety Analysis**

Safety will be evaluated by the incidence of TEAEs, severity and type of TEAEs, changes from baseline in the subjects' clinical laboratory results, vital signs, and ECG's using the safety set. All clinical safety data will be listed by subject and assessment time points, including rechecks, unscheduled assessments, and early termination, chronologically.

Continuous variables will be summarized using n, mean, SD, minimum, median, and maximum. Frequency counts and percentages will be reported for categorical data when appropriate. Where individual data points are missing because of dropouts or other reasons, the data will be summarized based on reduced denominators.

##### **7.12.1 Adverse Events**

All AEs captured in the database will be listed in by-subject data listings including verbatim term, coded term, severity (1=Grade 1: Mild, 2=Grade 2: Moderate, 3=Grade 3: Severe or medically significant but not immediately life-threatening, 4=Grade 4: Life-threatening , 5=Grade 5: Death), relationship to study drug (related or not related) and action relative to the study drug mobocertinib. Study procedure taken due to AE will also be listed. All AEs occurring during this study will be coded using the MedDRA® Version 23.0. However, only TEAEs occurring after administration of the first dose of study drug and through the end of the study will be summarized.

A TEAE is defined as an AE that is starting or worsening at the time of or after study drug administration.

For each treatment, TEAEs will be tabulated by System Organ Class (SOC) and Preferred Term. Summary tables will include number of subjects reporting the AE and as percent of safety set by treatment. The most commonly reported non-serious TEAEs (i.e., those events reported by >5% of all subjects in each treatment, excluding SAEs) will also be summarized. For the list of all AE summary tables, see TFL Shell document.

In addition, TEAEs will be summarized as number of AEs and percentage of AEs for each treatment for the overview of TEAEs.

Additional TEAE summary tables will be presented by severity and relationship to study drug. If a subject has multiple AEs with different severity levels within the same term, the subject will be counted in the most severe category only. If a subject has both related and unrelated AEs with the same term, the subject will be counted as having related TEAEs.

Should any SAEs occur or AEs leading to study drug discontinuation they will be summarized the same way as TEAE. All AEs will be displayed in the data listings and TEAEs will be discussed in the text of the Clinical Study Report (CSR).

### **7.12.2 Clinical Laboratory Evaluations**

Hematology, serum chemistry, and urinalysis will be performed at screening, check-in (Day -1) of each period, Day 4 of each period or prior to early termination from the study, and at the end of Period 2. In addition, laboratory safety tests may be performed at various unscheduled time points, if deemed necessary by the PI.

For all laboratory values that are numeric, summary statistics (n, mean, SD, minimum, median, and maximum) will be presented for each laboratory test by treatment and assessment time points. Change from baseline will be summarized. Baseline is defined as the last assessment including rechecks taken prior to the first dosing in each period (Day -1).

For each laboratory test, a shift table will be developed comparing the frequency and percentage of the results at baseline (above normal (H), normal (N), or below normal (L)) with the postdose time points. For urinalysis tests, the categories are normal (N) and abnormal (A). Out-of-range values and corresponding recheck results will be listed.

Out-of-normal range flags will be recorded as follows: high (H) and low (L) for numerical results and did-not-match (\*) for categorical results. If a value fails the reference range, it will automatically be compared to a clinically significant (CS) range. If the value falls within the CS range, it will be noted as "N" for not clinically significant. If the value fails the CS range, it will be flagged with a "Y" which prompts the PI to determine how the out-of-range value should be followed using 4 Investigator flags: "N", not clinically significant, "R", requesting a recheck, "^", checking at the next scheduled visit, or "Y", clinically significant. Additionally, the PI will

provide a 4th flag when the 3rd flag indicates “R” or “^”. This 4th flag is intended to capture final CS (+)/NCS (-) when the 3rd flag does not document significance. All clinically significant laboratory tests, as indicated by the PI, and the corresponding values will be listed by subject. All clinical laboratory data will be presented in by-subject data listings. CS results will also be presented in a table.

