3.0 SCHEDULE OF STUDY PROCEDURES

Study Procedures ^a	S ^b	Study Days in Periods 1 and 2 ^c														EOS or ET ^p	FU ^q	
		Days in Period →		1										2	3	4	6	
		Hours →	C-I ^d	0	0.5	1	2	4	6	8	12	24	48	72	120	168	240	
Administrative Procedures																		
Informed Consent	X																	
Inclusion/Exclusion Criteria	X	X ^f																
Medical History	X																	
Safety Evaluations																		
Full Physical Examination ^g	X																	
Height	X																	
Weight	X	X ^h																
12-Lead Safety ECG	X		X ^k					X									X	
Vital Signs (HR and BP)	X		X ^k					X			X	X					X	
Vital Signs (RR and T)	X																X	
Pulmonary function test ^l	X																	
Hem, Serum Chem ^j , and UA	X	X ^l										X					X	
Serum Pregnancy Test (♀ only)	X	X																
Serum FSH (PMP ♀ only)	X																	
Urine Drug and Alcohol Screen	X	X																
HIV/Hepatitis Screen	X																	
AE Monitoring	X											X						
ConMeds Monitoring												X						

CONFIDENTIAL

Study Procedures ^a	S ^b	Study Days in Periods 1 and 2 ^c													EOS or ET ^p	FU ^q	
		-1		1							2	3	4	6	8	11 ^e	
		Hours →	C-I ^d	0	0.5	1	2	4	6	8	12	24	48	72	120	168	240
Study Drug Administration / PK																	
TAK-788 Administration				X													
Blood for TAK-788 and metabolites (AP32960 and AP32914) PK				X ^m	X	X	X	X	X	X	X	X	X	X	X	X ⁿ	
Other Procedures																	
Confinement in the CRU ^o										X							
Visit and Return Visits	X																

- a. For details on Procedures, refer to Section 9.0.
- b. Within 21 days prior to the first study drug administration.
- c. There will be a washout period of 10 days between the dose in Period 1 and the dose in Period 2.
- d. Subjects will be admitted to the CRU on Day -1 of Period 1, at the time indicated by the CRU.
- e. Day 11 of Period 1 will be the same as Day 1 of Period 2. Study procedures will only be performed once.
- f. To be conducted in Period 1 only.
- g. Symptom-driven physical examinations may be performed at other times, at the PI's or designee's discretion.
- h. If the screening assessment was conducted within 4-7 days prior to the first dosing (Day 1 of Period 1), assessment will be conducted at check-in only if, in the opinion of the Investigator, there is reason to believe they have substantially changed.

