- i. Pulmonary function tests may be performed in the event of a pulmonary AE and deemed clinically necessary, as determined by the Investigator or designee.
- j. Samples for serum chemistry will be obtained following a fast of at least 8 hours, however, in case of dropouts or rechecks, subjects may not have fasted for 8 hours prior to the serum chemistry sample being taken.
- k. To be performed within 24 hours prior to dosing.
- l. To be repeated prior to dosing in Period 2.
- m. Prior to dosing.
- n. The Period 1 Day 11 PK sample will serve as the pre-dose PK sample for Period 2.
- o. Subjects will start confinement on Day -1 of Period 1 and will be released from confinement after the 240-hour study assessments in Period 2 are completed. At all times, subjects may be required to remain at the CRU for longer at the discretion of the Investigator or designee.
- p. To be performed at the end of Period 2 or prior to early termination from the study.

Study Procedures ^a		S ^b	Study Days in Periods 1 and 2 ^c														
Days in Period →			-1	1							2	3	4	6	8	11 ^e	
Hours →	C-I ^d		0	0.5	1	2	4	6	8	12	24	48	72	120	168	240	EOS or ET ^p

q. The clinic will contact all subjects (including subjects who terminate the study early) 30 ± 2 days after the last TAK-788 dose to determine if any AEs have occurred since the last study visit.

Abbreviations: ♀ = Females, AE = Adverse events, BP = Blood pressure, C-I = Check-in, Chem = Chemistry, ConMeds = Concomitant medication, CRU = Clinical research unit, ECG = Electrocardiogram, EOS/ET = End-of-Study or early termination, FSH = Follicle-stimulating hormone, FU = Follow-up, Hem = Hematology, HIV = Human immunodeficiency virus, HR = Heart rate, PI = Principal Investigator, PK = Pharmacokinetics, PMP = Postmenopausal, Preg = Pregnancy, RR = Respiratory rate, S = Screening, T = Temperature, UA = Urinalysis

Table 3.a Pharmacokinetic Plasma Concentration Sampling Schedule

Study Day	Sample Collection Time	Time (Relative to Dosing) h:min	Plasma Concentrations of TAK-788, AP32960, and AP32914
1 (Period 1)	0 h (predose)	00:00 ^a (predose)	✓
	0.5 h	00:30 (±5 min)	✓
	1 h	01:00 (±10 min)	✓
	2 h	02:00 (±10 min)	✓
	4 h	04:00 (±10 min)	✓
	6 h	06:00 (±20 min)	✓
	8 h	08:00 (±20 min)	✓
	12 h	12:00 (±20 min)	✓
	2	24:00 (±30 min)	✓
	3	48:00 (±30 min)	✓
4	0 h	72:00 (±60 min)	✓
6	0 h	120:00 (±60 min)	✓
8	0 h	168:00 (±60 min)	✓
11 (Predose Day 1 Period 2)	0 h	240:00 (±60 min) ^{a,b} (predose)	✓
	0.5 h	00:30 (±5 min)	✓

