### **4.4 Study Design**

This is an open-label, randomized, 2-period, and 2-sequence crossover high-fat meal effect study in healthy adult subjects.

Subjects will undergo screening evaluations to determine eligibility within 21 days prior to dosing. Subjects will be admitted to the clinical facility the day prior to dosing in each period (Day -1). Subjects will be randomized on Day 1 of Period 1 to a crossover sequence in a 1:1 ratio and administered a single oral dose of 160 mg of mobocertinib with or without a high-fat meal on Day 1 of each period (i.e., Period 1 and Period 2). Each dose will be separated by a washout period of 10 days. Blood samples for mobocertinib PK will be collected predose and up to 240 hours following each mobocertinib dose.

Subjects will receive the following treatments on one occasion in a crossover fashion to evaluate the effect of a high-fat meal:

- Treatment A: Administration of a single oral dose of 160 mg mobocertinib (4 x 40 mg capsules) following an overnight fast.
- Treatment B: Administration of a single oral dose of 160 mg mobocertinib (4 x 40 mg capsules) with a high-fat meal.

\* 800-1000 total calories, 500-600 calories, 55-65 g, or 50% from fat

Subjects will remain at the clinical site until the 240-hour study assessments in Period 2 are completed. All doses of mobocertinib will be administered at the clinic during this study. A final safety follow-up phone call will occur  $30 \pm 2$  days after the last mobocertinib dose to determine if any adverse events (AEs) have occurred since the last study visit. Replacement of discontinued or withdrawn subjects due to any reason will be assessed on a case by case basis by the Sponsor and the Principal Investigator (PI) to ensure a minimum of 12 PK-evaluable subjects complete the study.

Any subject who experiences emesis within 8 hours postdose will be excluded in the final PK data analysis and may be replaced with a new subject.

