## **7.1.1 Study Definitions**

### **7.1.1.1 Definition of Study Days**

Day 1 for each period is defined as the date on which a subject is administered their first dose of the study drug in each period. Other study days are defined relative to Day 1 with Day -1 being the day prior to Day 1 of each period. Study day prior to the first dose of each treatment will be calculated as: date of assessment-date of first dose in each period; study day on or after the date of first dose will be calculated as: date of assessment-date of first dose in each period +1.

For all clinical laboratory evaluations, vital signs, and 12-lead ECGs, baseline is defined as the last assessment including rechecks taken prior to mobocertinib dosing at each period.

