### **7.12.4 12-Lead ECGs**

12-lead ECGs will be recorded at screening, predose (Day -1), 4 hours of Day 1 postdose (time relative to mobocertinib dose) or upon early termination, and at the end of Period 2. Additional unscheduled ECGs may be recorded at other times if deemed necessary by the PI.

Summary statistics (n, mean, SD, minimum, median, and maximum) will be reported for ECG results and change from baseline by treatment and time point of collection. Baseline is defined as the last assessment including rechecks taken prior to dosing in each period (Day -1). ECG data will also be displayed in a data listing by subject.

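### Safety values taken before the Period 2 dose serve only as Period 2 baseline, so late changes after the Period 1 dose are not tabulated as post-dose changes or laboratory shifts

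*SAP*

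**What the plan says.** **Timing.** SAP 4.4 states: "Each dose will be separated by a washout period of 10 days". Footnote e to the schedule in Protocol 3.0 makes the last day of Period 1 and the dosing day of Period 2 one and the same: "Day 11 of Period 1 will be the same as Day 1 of Period 2. Study procedures will only be performed once". The predose ECG, heart rate and blood pressure carry the footnote "To be performed within 24 hours prior to dosing", and the check-in laboratory tests carry "To be repeated prior to dosing in Period 2".

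**Baseline.** SAP 7.1.1.1 gives one rule for laboratory tests, vital signs and ECGs: "baseline is defined as the last assessment including rechecks taken prior to mobocertinib dosing at each period". SAP 7.12.2 repeats it for laboratory tests: "Baseline is defined as the last assessment including rechecks taken prior to the first dosing in each period (Day -1". SAP 7.12.4 does so for ECGs: "Baseline is defined as the last assessment including rechecks taken prior to dosing in each period (Day -1". SAP 7.12.3 treats vital signs in the same way.

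**Tables.** Change from baseline is summarised by treatment and time point for laboratory tests, ECG, heart rate and blood pressure. A shift table, comparing baseline with post-dose time points, is planned for laboratory tests only.

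**PK, for contrast.** The sample taken on the shared day has two roles: "The Period 1 Day 11 PK sample will serve as the pre-dose PK sample for Period 2". It is both the 240-hour value of Period 1 and the predose value of Period 2.

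**The concern.** The value obtained just before the second dose is the only scheduled late look at the first dose. The SAP uses it as the reference for Period 2 and nowhere assigns it to the Period 1 treatment as a post-dose time point.

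Take a laboratory test that is normal at the Period 1 baseline and on Day 4 of Period 1, high before the Period 2 dose, and still high on Day 4 of Period 2. The shift table shows normal to normal under the first treatment and high to high under the second. If the value has returned to normal by Day 4 of Period 2, it reads as an improvement under the second treatment. In neither case is there a post-dose shift under the treatment that preceded the rise.

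At stake is how complete the by-treatment safety summaries are. Each treatment's late post-dose row rests only on the subjects who received that treatment second, although the corresponding value is collected for the others too.

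**Working it through.** The plan states no figure for this point, so the check is a mapping of assessments to doses followed by a simple count.

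**Step 1: when the pre-Period-2 values fall.** The dose interval is 10 days = 240 h. ECG, heart rate and blood pressure are taken within 24 h before dosing, so between 240 − 24 = 216 h and 240 h after the Period 1 dose. The SAP places the laboratory tests on Day -1 of Period 2, about 9 days after the Period 1 dose.

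**Step 2: scheduled values the SAP can tabulate as post-dose (SAP 7.12.2 to 7.12.4).**

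| Data | After Period 1 dose | After Period 2 dose |
|---|---|---|
| Laboratory tests | Day 4 (72 h) | Day 4, end of Period 2 |
| Heart rate, blood pressure | 4 h, 12 h, Day 2 (24 h) | the same, plus end of Period 2 |
| ECG | 4 h | 4 h, end of Period 2 |

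Only the Period 2 dose has a late value. A subject who leaves after Period 1 has an early-termination assessment that could count as post-dose, so the gap concerns subjects who continue.

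**Step 3: subjects with a late post-dose value, per treatment.** Inputs are 14 subjects (Protocol 1.0) and 1:1 allocation to AB and BA (Protocol 8.1.4), hence 7 and 7 if all are dosed and complete. I assume that end-of-Period-2 values are tabulated under the Period 2 treatment; the SAP does not say so expressly.

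- As written: 0 of 14 after the Period 1 dose and 14 of 14 after the Period 2 dose, which is 7 of 14 per treatment.
- With the pre-Period-2 value in both roles: 14 of 14 per treatment.

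**Step 4: what that means for a treatment's table.** Let p be the probability that a subject has a late abnormality after a given treatment. The documents give no rate, so p is an assumption and a range is shown. The chance that the table shows at least one is 1 − (1 − p)^n.

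| Assumed p | n = 7 (as written) | n = 14 (both roles) |
|---|---|---|
| 2% | 0.13 | 0.25 |
| 5% | 1 − 0.95^7 = 0.30 | 1 − 0.95^14 = 0.51 |
| 10% | 1 − 0.90^7 = 0.52 | 1 − 0.90^14 = 0.77 |
| 20% | 0.79 | 0.96 |

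With 12 completers (6 versus 12 per treatment), the figures are 0.26 versus 0.46 at 5% and 0.47 versus 0.72 at 10%.

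**The case against.** **The data are not lost.** A reader might infer that a late abnormality after the first dose is reported nowhere. The documents do not support that. SAP 7.12 lists all safety data by subject in chronological order, and with 14 subjects such a sequence can be read directly. The pre-Period-2 value is in the by-time-point summaries, though under the Period 2 label. SAP 7.12.2 also gives clinically significant laboratory results a table. Under Protocol 10.1 a laboratory or ECG change judged clinically significant may be recorded as an AE, and would then be counted as a TEAE. This stands, and it lowers the weight of the point. What it leaves uncovered is a late change not judged clinically significant, or a modest group-level one, which change and shift summaries are meant to show.

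**Shift tables.** A reader might also take the gap to cover shift tables for all three data types. Only laboratory tests have one. An abnormal pre-Period-2 result does enter it, as a baseline category.

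**Liver tests.** Inclusion criterion 4 requires ALT, AST, ALP and total bilirubin to be at or below the upper limit of normal at screening and first check-in. A high Period 2 baseline in these four must therefore have arisen after entry, and an attentive reader could work that out. Other tests have no such numeric limit.

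**Pooling exposures.** It is tempting to compare 14 with 28 exposures, which gives larger probabilities. That pools the treatments and treats two exposures of one subject as independent, while the tables are by treatment. The 7-versus-14 comparison is the relevant one.

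**The baseline rule is defensible.** A period-specific baseline isolates change after that period's dose, and nothing here argues against it.

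**Unseen material.** The SAP does not enumerate the post-dose time points of the shift table, and the table shells are not available. The shells could close the gap; the SAP text does not.

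**Conclusion.** The point holds as a gap in table mapping. For subjects who proceed to Period 2, the SAP text does not tabulate a late change after the Period 1 dose as a post-dose change from baseline (laboratory tests, ECG, heart rate and blood pressure) or as a shift (laboratory tests). Late post-dose values number about 7 of 14 per treatment where 14 of 14 are available. At assumed rates of 5% and 10%, the chance that a treatment's table shows at least one late abnormality is 0.30 rather than 0.51, and 0.52 rather than 0.77.

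These figures rest on equal sequences, all 14 subjects completing, end-of-Period-2 values being assigned to the Period 2 treatment, and event rates that the documents do not supply. They describe visibility in one type of table, not detection overall. Priority is modest: safety is an exploratory objective, the listings hold every value, and the primary PK analysis is unaffected.

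**What to change.** Keep the period-specific baseline. In SAP 7.12.2 to 7.12.4:

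- Also tabulate the last value before the Period 2 dose as the late post-dose time point of the Period 1 treatment, with change from the Period 1 baseline and, for laboratory tests, the shift from it. This mirrors the dual role of the PK sample.
- State that end-of-Period-2 values belong to the Period 2 treatment.
- Align the table shells with this wording.

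I would not add a comparison of Period 2 values with the Period 1 predose value. It would place the combined effect of both doses under the Period 2 treatment and be hard to interpret.

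The cost is a few sentences in the SAP and one more time point in existing tables. No assessment, visit or subject is added.

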### **7.12.3 Vital Signs**

Single measurements of heart rate and blood pressure will be obtained at screening, predose (Day -1), 4 and 12 hours of Day 1, and Day 2 postdose (times relative to mobocertinib dose) in each period or upon early termination, and at the end of Period 2. Respiration rate and temperature will only be collected at screening. Additional unscheduled vital signs measurements may be taken at other times, if deemed necessary by the PI.

Summary statistics (n, mean, SD, minimum, median, and maximum) will be reported for vital sign results and change from baseline by treatment and time point of collection. Baseline is defined as the last assessment including rechecks taken prior to dosing in each period (Day -1). Change from baseline will not be calculated for respiratory rate and temperature. Vital signs will also be displayed in a data listing by subject.

### **7.12.4 12-Lead ECGs**

12-lead ECGs will be recorded at screening, predose (Day -1), 4 hours of Day 1 postdose (time relative to mobocertinib dose) or upon early termination, and at the end of Period 2. Additional unscheduled ECGs may be recorded at other times if deemed necessary by the PI.

Summary statistics (n, mean, SD, minimum, median, and maximum) will be reported for ECG results and change from baseline by treatment and time point of collection. Baseline is defined as the last assessment including rechecks taken prior to dosing in each period (Day -1). ECG data will also be displayed in a data listing by subject.

### **7.12.5 Pulmonary Function Test**

Pulmonary function tests (PFTs) may be performed in the event of a pulmonary AE and deemed clinically necessary, as determined by the PI. PFT results if present will be presented in a data listing by subject.

### **7.12.6 Physical Exams**

A full physical exam will be performed at screening. Symptom-driven physical exams may be performed at other times at the discretion of the PI. Physical exam findings will be presented in a data listing by subject. Reproductive system findings will also be listed by subject.

### **7.12.7 Overdose**

All cases of overdose will be presented in a data listing by subject. Any AEs associated with overdose will be documented as AEs.

### **7.13 Interim Analysis**

Not applicable.

